9.1.4. Risk factors for RSV LRTI

- Age (continuous)
- Male sex (M/F)
- Small for gestational age (Continuous)
- Congenital anomalies with internal structural defects and/or with functional defects (Y/N)
- Household composition (number of people living in household) (continuous)
- How many children under age of 6 live in household (continuous)
- Cigarette smoking during pregnancy (Y/N)
- Born during RSV transmission season (Y/N)
- Alcohol consumption during this pregnancy (Y/N)
- Highest education level of mother (Y/N)

9.1.5. RSV Seasonality

Table 11 RSV Transmission seasons by country/region and centre

Country/region	Seasonality	Centre #
Thailand		PPD
Bangkok	June-October	
Chiang Mai	July-November	
Malaysia		
Selangor	Year round	
Kota Kinabalu	Year round	
Alor Setar	Year round	
Kuching	Year round	
Philippines		
Manila	Year round	
Cebu	Year round	
South Africa		
Parow, Western Cape	April-August	
Pretoria, Gauteng	February-June	
	February-August	
Panama		
David	May-January	
Panamá	May-January	
Chorrera	May-January	
Bangladesh		
Matlab	July-December	
Kamlapur	July-February	
Brazil		
Ribeirao Preto/SP	March-July	
Belo Horizonte/MG	March-July	
Nata/RN	March-July	
Argentina		
Buenos Ares	May-July	
Cordoba	May-July	
Mendoza	May-July	
Colombia		
Medellin	Mar-Jun & Sep-Nov	
Medellin	Year round	
Bogota	Year round	
Bogota	Mar-May	
Cali	April-Jun	
Villavicencio	Mar-Apr/May & Nov-Dec	
Mexico		
Monterrey	September-April	
Oaxaca	September-April	
Durango	September-April	

9.2. Data presentation

The following decimal description will be used for the analyses.

Table 12 Decimal points in analyses

Display Table	Parameters	Number of decimal digits
All summaries	% of frequency, including LL & UL of CI	1
All summaries	% frequency, including LL & UL of CI	1
All summaries	Mean, median, minimum, maximum	1
All summaries	SD	2
All summaries	P-value	3

9.3. Subgroup definitions

The following sub-group names will be used for statistical analyses:

Sub-group order in tables	Sub-group label in tables	Sub-group definition for footnote
Country		
1	TH	Subjects from Thailand
2	MY	Subjects from Malaysia
3	PH	Subjects from Philippines
4	SA	Subjects from South Africa
5	BD	Subjects from Bangladesh
6	PA	Subjects from Panama
7	BR	Subjects from Brazil
8	AR	Subjects from Argentina
9	CO	Subjects from Colombia
10	MX	Subjects from Mexico
Region		
Latin America	LatAM	Subjects from Brazil, Argentina, Colombia, Mexico, Panama
Asia Pacific	AsiaPac	Subjects from Thailand, Malaysia, Philippines, Bangladesh
South Africa	SA	Subjects from South Africa
Age category maternal subject at enrolment		
1	18-34	18-34 years of age
2	≥35	35 years of age or older
Age category infant (3 categories)		
1	0-2	Birth to one day before the 3rd month of life (0-30 days)
2	0-5	Birth to one day before the 6th month of life (0-180 days)
3	0-11	Birth one day before the 12th month of life (0-365 days)
Age category infant (One-month intervals)		
1	0	Birth to one day before the 1 st month of life
2	1	First day of 1 month to one day before the 2 nd month of life
3	2	First day of 2 months to one day before the 3 rd month of life
4	3	First day of 3 months to one day before the 4 th month of life
5	4	First day of 4 months to one day before the 5 th month of life

Sub-group order in tables	Sub-group label in tables	Sub-group definition for footnote
6	5	First day of 5 months to one day before the 6 th month of life
7	6	First day of 6 months to one day before the 7 th month of life
8	7	First day of 7 months to one day before the 8 th month of life
9	8	First day of 8 months to one day before the 9 th month of life
10	9	First day of 9 months to one day before the 10 th month of life
11	10	First day of 10 months to one day before the 11 th month of life
12	11	First day of 11 months to one day before the 12 th month of life

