5.3.6.2. Additional considerations

A correction from the analysis planned in protocol in section 5.3.6.1 is that we will be reporting on all cause LRTIs and RSV associated LRTIs.

This analysis will be based on the infant PPS and will be done on the first episode of all, of severe, and of very severe RSV LRTIs (Section 2.2).

Incidence analyses will be performed overall, by country and by age strata (0-2 months, 0-5 months, and 0-11 months). If applicable (in the case of low numbers of incidence), incidence analyses will also be presented by region (Section 9.3). Incidence rates will also be calculated in one-month intervals from birth to one year of age, please see the monthly infant age intervals in Section 9.3.

The analysis of RSV disease incidence is summarized in the table below showing endpoints and analytic methods, these include incidence rate, proportion affected, and incidence proportion.

Incidence rate is the number of first events per person time. Incidence proportion is the number of first RSV LRTI over population at risk during the specified time period (0-2 months, 0-5 months and 0-11 months). Proportion affected is the number of subjects with at least one episode of RSV LRTI at age interval over the total number of subjects at the start of the age interval.

For each of the RSV LRTI endpoints listed in [Table 11](#), the 95% CI will be computed as described in section [9.5.2](#). Kaplan-Meier curves presenting the cumulative probability of the first episode will be displayed overall. The cumulative probability of presenting the first episode will be given with its 95% CI at the end of the follow-up.

Frequencies of repeat occurrences of RSV LRTI, severe LRTI and very severe LRTI will be tabulated.

Cumulative incidence will be presented from birth to one year of life by monthly intervals (Subgroups in section [9.3](#)).

Table 6 Summary of RSV incidence analyses for RSV LRTI of infants from birth to 1 year (Visit 1-NB to visit 4-NB)

Endpoints	Incidence analysis method	Subgroup
All RSV LRTI Severe RSV LRTI Very Severe RSV LRTI	Incidence rates of first episode Cumulative probability of first episode (Kaplan Meier)	Overall, by country, and by age strata
All RSV LRTI Severe RSV LRTI Very Severe RSV LRTI	Proportion affected by all new episodes	Overall, by country, and by age strata
All RSV LRTI Severe RSV LRTI Very Severe RSV LRTI	Incidence proportion of first episode	Overall and by country within each age strata)

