When considering RSV antibodies in cord blood, we are only considering RSV-A antibodies at this time (however, in the future we might also consider RSV-B antibodies). When considering RSV positivity status in nasal swabs, we consider positivity for RSV-A or RSV-B.

This analysis will be performed on the Infant PPS and will be done on the first episode (not recurrent events) of RSV LRTIs occurring during the following age intervals: 0-2 months and 0-5 months.

Step 1: Descriptive analysis:

Descriptive analyses (seropositivity rate with 95% CIs, geometric mean, median, min, max) of RSV-A neutralizing antibodies in the baseline cord blood samples will be analysed in only those with RSV positive nasal swab samples.

Next, descriptive analyses (seropositivity rate with 95% CIs, geometric mean, median, min, max) of RSV-A neutralizing antibodies in the baseline cord blood samples will be presented by RSV LRTI, RSV severe LRTI, and RSV very severe LRTI case statuses.

In addition, if further exploration is desired, we may plot levels of RSV A vs RSV-B neutralizing antibodies in cord blood among RSV LRTI positive and negative infants to see if any patterns are observed.

Step 2: Cox models:

The impact of the level of RSV neutralizing antibodies in the baseline cord blood samples on the incidence of first event of RSV-LRTI, RSV-severe LRTI and RSV very severe LRTI separately will be assessed through Cox models.

Cox regression models will be performed for the univariate analyses to obtain unadjusted hazards ratios of the determinants of interest.

Next a multivariable Cox regression model will be performed to estimate the relative contribution of each potential risk factor adjusting for the simultaneous effects of the other covariates. The model will include: time-independent covariates (e.g. gender, etc.) and time-dependent covariates (age). Covariate selection will be done using backward elimination and statistical significance. Potential risk factors will be included in the multivariable models if univariate p-value will be less than 0.1 and the multivariable model will be performed only if the number of events is sufficient (at least 10 events per covariate). In addition, depending on the data, other models could be explored or the model could be simplified.

The following covariates in infants may be considered in the multivariable models:

- Age (continuous)
- Male sex (M/F)
- Small for gestational age (Continuous)

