10.1.1. Age

Age of infant will be expressed in months and will be computed as the number of complete calendar months between the date of birth (DOB) and the date of event. For example:

DOB = 10JUN2017, Date of event = 09JUL2018 -> Age = 12 months

DOB = 10JUN2017, Date of event = 10JUL2018 -> Age = 13 months

Age of the mother at the time of childbirth will be expressed in years and will be computed as the number of complete calendar years between the birth date of the infant and the birth date of the mother. For example:

DOB = 10SEP1983, Date of vaccination = 09SEP2018 -> Age = 34 years

DOB = 10SEP1983, Date of vaccination = 10SEP2018 -> Age = 35 years

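### SAP 9.3 gives the 0-2 month infant stratum two incompatible windows: up to 3 months in words, 0-30 days in brackets

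*SAP*

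**What the plan says.** The subgroup table in SAP section 9.3 has three cumulative infant age strata. The first, labelled 0-2, reads "Birth to one day before the 3rd month of life (0-30 days". The second, labelled 0-5, reads "Birth to one day before the 6th month of life (0-180 days", and the third, labelled 0-11, reads "Birth one day before the 12th month of life (0-365 days". The same table then lists twelve one-month intervals. Interval 0 is "Birth to one day before the 1 st month of life" and interval 2 is "First day of 2 months to one day before the 3 rd month of life".

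Section 10.1.1 says infant age is "computed as the number of complete calendar months between the date of birth (DOB) and the date of event".

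The 0-2 month stratum is used in several places:
- Section 5.3.6.2 runs the RSV-LRTI incidence analyses (all, severe, very severe) "by age strata (0-2 months, 0-5 months, and 0-11 months"; section 5.4.3 repeats them with the alternative case definitions.
- Section 5.4.1.2 uses the same three strata for co-infections.
- Section 5.4.2.2 limits the cord-blood antibody analysis to first episodes "occurring during the following age intervals: 0-2 months and 0-5 months".
- Section 5.3.7.2 reports RSV hospitalization by age strata without listing them.

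**The concern.** One row carries two windows that differ by a factor of about three. The bracket is the only explicit numeric bound in that row, so it is easy to code from, and nothing in the SAP gives precedence to the words or to the days.

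The 0-2 month window is one of three cumulative reporting windows for RSV-LRTI incidence and one of only two for the cord-antibody models. The study is meant to inform maternal RSV vaccine trials (section 2.1), where incidence in the first three months is a natural planning figure. A first-month result printed as a three-month result would mislead those readers. So would a correct three-month result with a 0-30 day footnote, because they could not tell which window they had.

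**Working it through.** **Step 1. Which part of the row is wrong?** Take birth as day 0 and count completed calendar months as in section 10.1.1. Over 730 consecutive birth dates, the last day before each age is:

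| Worded end | Last day before it (range) | Mean | Bracket in 9.3 |
|---|---|---|---|
| 1 month (interval 0) | 27-30 | 29.5 | none given |
| 3 months (stratum 0-2) | 88-91 | 90.4 | 0-30 |
| 6 months (stratum 0-5) | 180-183 | 181.7 | 0-180 |
| 12 months (stratum 0-11) | 364-365 | 364.5 | 0-365 |

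The 6- and 12-month brackets reproduce, give or take a few days. The 3-month bracket does not; it matches interval 0. A bracket of 0-90 would have reproduced.

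**Step 2. Could the wording mean something shorter?** If the third month of life were taken to begin after two completed months, the window would end at about day 60. The same reading would end the other strata at about 5 × 30.4375 = 152 days and 11 × 30.4375 = 335 days, not 180 and 365. It also conflicts with interval 2, which starts at 2 months and closes at the same worded bound. And it still does not give 30.

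**Step 3. Share of the window lost if the bracket is applied.** Counting days inclusively, 0-30 is 31 days and 0-90 is 91 days.
- Kept: 31/91 = 0.341.
- Lost: 60/91 = 0.659.
- For end days 88 to 91: 1 − 31/89 = 0.652 to 1 − 31/92 = 0.663.

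**Step 4. Effect on events.** The SAP gives no expected rate, so the rates below are assumptions, with 2300 infants (the approximate maximum in section 2.1), no dropout and a constant hazard r. First events = 2300 × (1 − exp(−r × days/365.25)). The last column applies the SAP's minimum of 10 events per covariate.

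| Assumed rate per 100 person-years | Events, 31 days | Events, 91 days | Covariates allowed, 31 vs 91 days |
|---|---|---|---|
| 2 | 3.9 | 11.4 | 0 vs 1 |
| 5 | 9.7 | 28.5 | 0 vs 2 |
| 10 | 19.4 | 56.6 | 1 vs 5 |
| 20 | 38.7 | 111.8 | 3 vs 11 |

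The ratio of events is 0.34 to 0.35 throughout. Proportions with a fixed denominator at birth fall in the same ratio.

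**Step 5. Effect on the incidence rate.** Section 9.5.1 divides first episodes by person-time. If both use 31 days, a constant hazard leaves the rate essentially unchanged; with a hazard that varies by age, it is the first-month rate. If one uses 31 days and the other 91, the rate is wrong by about 91/31 = 2.9-fold: too low if the numerator is the truncated part, too high if the person-time is.

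**The case against.** The strongest reply is that the intended window can be recovered from the row itself. The label, the words, the one-month intervals, the months named in sections 5.3.6.2, 5.4.1.2 and 5.4.2.2, and the age rule in 10.1.1 all agree on three months. The column holding the bracket supplies footnote text, while the derivation rule sits in 10.1.1. A programmer who follows 10.1.1 loses nothing. The stratum serves secondary and tertiary analyses only, and no primary objective depends on it.

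Most of this stands. A reader might infer that the SAP simply defines the stratum as 0-30 days, so that every 0-2 month analysis loses two thirds of its data. The document does not support that: the row contradicts itself, and the loss arises only if the bracket is followed. Nor would a consistently windowed incidence rate fall by two thirds. The one-month interval rates and the monthly cumulative incidence do not use this bracket, and they would help to expose a truncated 0-2 row.

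A reader might also treat 0-180 and 0-365 days as errors of the same kind. They are roundings: 180 days is 0 to 3 days short of the calendar bound, and 365 overshoots by at most one day.

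What the reply does not remove is that no sentence ranks the words above the days, and that the footnote text is false even when the programming is right.

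**Conclusion.** The point holds as an internal contradiction in one row of section 9.3, with a wrong numeric bound on an analysis window. The bracket should correspond to about 0-90 days.

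- **If the bracket governs:** about 66% of the window is lost (65.2% to 66.3% depending on birth date). Under a constant hazard, counts, proportions affected, incidence proportions and Cox-model events for the stratum fall to about one third; a hazard that rises after the first month would make the loss larger. The rate becomes a first-month rate, or is off about 2.9-fold if the windows are mixed.
- **If the words govern:** the estimates are correct and only the footnote is wrong.

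The share of days lost is plain arithmetic. The event counts rest on assumed rates and full follow-up, so they show scale only. Which window was actually programmed cannot be known from the SAP. The row should be corrected before the 0-2 month tables are produced.

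**What to change.** In section 9.3, replace the 0-30 day bracket with age under 3 completed calendar months under 10.1.1 (about 0-90 days). State that the same window applies to the numerator and to the person-time or denominator for that stratum. Check that the programmed flag and the table footnotes match.

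Expressing the 0-5 and 0-11 strata as under 6 and under 12 completed months would make all three rows consistent, but that is optional tidying.

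The cost is a one-row text correction and a check of one derived variable. No further data are needed.

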9.4. Case definitions

Please refer to section 2.1 for an explanation of how data is collected for surveillance in this study since that is the data that will be used for the derivation of case definitions.

Note that if a worsening visit(s) takes place for the same episode, then all symptoms collected from the initial visit and the worsening visit(s) are combined and counted under one episode, with the most severe level of the symptoms being used in the case definition derivation. For example, if SpO₂ is collected in a case assessment and a worsening visit for the same episode, then the lowest SpO₂ from any visit will be used for the case definition derivation. This is done because the most severe level of a symptom will not necessarily be in the worsening form, so multiple scenarios of visits and data collection can be accounted for. The earliest date of a reported symptom will be used as the start date of the episode. The latest date of a reported symptom will be used as the end date of episode.

If an infant comes in for a visit with new bouts of cough or blocked nose after 7 days of his/her latest end date of an RTI symptom, then a new case assessment form is opened and this is potentially the start of a new episode.

Variables from a Case Assessment Visit will be pulled from [frmASSESSMENT_INFO], [frmSYMPTOMS_RTI], and [frmVITALSIGNS_RTI].

Variables from a Worsening Visit will be pulled from [frmWORSENING_INFO] and [frmVITALSIGNS_WOR].

9.4.1. RSV RTI

The child will be reported positive for RSV RTI when he/she presents with at least one of the following symptoms: (data pulled from the Case Assessment Visit)

- Runny nose reported during the case assessment visit. Variables will be pulled from [frmSURVEILLANCE_CONTACT] (field [ASSESS_VIS]= 'YES') and [frmSYMPTOMS_RTI] (fields [ASSESS_VIS]= 'Yes') and [frmSYMPTOMS_RTI] (fields[ASSESS_VIS]= 'Yes' and [sctSYMPTOMS_RTI]=[RUNNY])

- Blocked nose reported during the case assessment visit. Variables will be pulled from [frmSURVEILLANCE_CONTACT] (field [ASSESS_VIS]= 'YES') and [frmSYMPTOMS_RTI] (fields [ASSESS_VIS]= 'Yes') and [frmSYMPTOMS_RTI] (fields[ASSESS_VIS]= 'Yes' and [sctSYMPTOMS_RTI]=[BLOCKED]) Cough reported during the case assessment visit. Variables will be pulled from [frmSURVEILLANCE_CONTACT] (field [ASSESS_VIS]= 'YES') and [frmSYMPTOMS_RTI] (fields [ASSESS_VIS]= 'Yes' and [sctSYMPTOMS_RTI]= 'COUGH')

AND confirmed RSV infection

9.4.2. RSV LRTI

The child will be reported positive for RSV LRTI when he/she presents with at least one of the following symptoms: (The data can be pulled from the Case Assessment Visit)

- Cough reported during the case assessment visit. Variables will be pulled from [frmSURVEILLANCE_CONTACT] (field [ASSESS_VIS]= 'YES') and [frmSYMPTOMS_RTI] (fields [ASSESS_VIS]= 'Yes' and [sctSYMPTOMS_RTI]= 'COUGH')
- Difficulty breathing reported during the case assessment visit. Variables will be pulled from [frmSURVEILLANCE_CONTACT] (field [ASSESS_VIS]= 'YES') and [frmSYMPTOMS_RTI] (fields [ASSESS_VIS]= 'Yes' and [sctSYMPTOMS_RTI]= 'BREATHING')

AND at least one of following symptoms: **(The data can be pulled from the Case Assessment Visit OR Worsening Visits. If worsening visits took place for this episode, the most severe value of SpO₂ or RR will be used, whether it was observed in the Case Assessment Visit or the Worsening Visit.)**

- SpO₂(<95% if altitude ≤2500m and <92% if altitude >2500m) during the physical examination of case assessment visit. (field [scOXYGEN_SATURATION_RTI] OR [scOXYGEN_SATURATION_WOR]=[SpO₂] < '95.0% or <92%')

OR

- RR increase (field [sctRESPIRATORYRATE_RTI]=[VSORRES_RESP] OR [sctRESPIRATORYRATE_WOR]=[VSORRES_RESP_WOR])

RR increase defined as:

- > 60/minute (< 2 months of age)
- > 50/minute (2 to < 12 months of age)
- > 40/minute (12 to 24 months of age)

AND

Confirmed RSV infection from a nasal swab test.

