- Sampling schedule for **neonates/infants:** Surveillance for RSV LRTI will be conducted in infants through the 12 month study period. During this 1-year post-birth surveillance period, for each RTI with suspicion of difficulty in breathing, or wheezing, or with parental concern, a nasal swab will be collected at a visit to assess potential RSV associated RTIs/LRTIs.
- Primary Completion Date (PCD): 42 days post-delivery/birth (i.e. Visit 6 for maternal subjects and Visit 2-NB for infant subjects) or last visit of Epoch 002.
- End of Study (EoS): Last testing results released of samples collected up to Visit 4-NB (assays related to primary and secondary endpoints).
- Duration of the study: Approximately 4.5 to 6 months for maternal subjects; approximately 1 year for infant subjects.
 - Epoch 001: Screening
 - Epoch 002: Primary starting at Visit 1 and ending 42 days post-delivery/birth (Visit 6 for maternal subjects and Visit 2-NB for infant subjects).*
 - Epoch 003: Follow-up of infants starting 43 days post-delivery/birth and ending at Visit 4-NB (1 year post-birth).

*Any safety and disease surveillance data collected after Visit 2-NB will be collected in Epoch 003.

Table 2 Study groups and epochs foreseen in the study

Study Groups	Number of subjects enrolled	Age (Min/Max)	Epochs		
			Epoch 001	Epoch 002	Epoch 003
Maternal subjects	Up to ~ 2300	18 years - 45 years	x	x	
Infants	Up to ~ 2300	NA		x	x

Approximately 200 to 300 per country. To achieve the enrollment targets noted above, the number of pregnant women SCREENED in each country may exceed the country-specific enrolment goal.

- Surveillance for pregnancy outcomes and pregnancy-related events of interest that occur from Visit 1 up to 42 days after delivery (Visit 6).
- Surveillance for neonatal events of interest that occur from birth up to 28 days of age.
- Surveillance for RSV LRTI and RSV hospitalization in infants, from birth up to 1 year of age. Nasal swabs will be collected during surveillance visits to confirm RSV positivity.

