9.4.3. RSV severe LRTI

RSV severe LRTI cases will be reported if the person meets the case definition of RSV LRTI

AND

(The data for below can be pulled from the Case Assessment Visit OR Worsening Visits. If worsening visits took place for this episode, the most severe value of SpO₂ or RR will be used, whether it was observed in the Case Assessment Visit or the Worsening Visit.)

- SpO₂(<93% if altitude ≤2500m and <90% if altitude >2500m) (field [scOXYGEN_SATURATION_RTI] OR [scOXYGEN_SATURATION_WOR]=[SpO₂]<‘93.0% or <90%’)
OR
- Lower chest wall indrawing reported during the physical examination. (field [sctCHEST_INDRAWING_RTI]=[INDRAWING]=‘YES’) OR (field [sctCHEST_INDRAWING_WOR]=[INDRAWING]=‘YES’)

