9.4.4. RSV very severe LRTI

RSV very severe LRTI is defined as meeting the case definition of RSV LRTI

AND

(The data for below for SpO₂ can be pulled from the Case Assessment Visit OR Worsening Visits. If worsening visits took place for this episode, the most severe value of SpO₂ or RR will be used, whether it was observed in the Case Assessment Visit or the Worsening Visit.)

- SpO₂(<90% if altitude ≤2500m and <87% if altitude >2500m) (field [scOXYGEN_SATURATION_RTI] OR [scOXYGEN_SATURATION_WOR]=[SpO₂]<‘90.0% or <87%’)
OR
- Inability to feed reported in signs and symptoms.
[sctSEVERITY_SIGNS_RTI]=[FEEDING]=‘Unable to feed’)
OR
- Failure to respond/unconscious reported in signs and symptoms.
[sctSEVERITY_SIGNS_RTI]=[CONSCIOUS]=‘The child is unresponsive to all stimuli’)

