9.4.7. All cause LRTI

All cause LRTI is reported if the child has one or more of the following:

- COUGH reported during the case assessment visit. Variables will be pulled from [frmSURVEILLANCE_CONTACT] (field [ASSESS_VIS]= 'YES') and [frmSYMPTOMS_RTI] (fields [ASSESS_VIS]= 'Yes' and [sctSYMPTOMS_RTI]= 'COUGH')
- Difficulty breathing reported during the case assessment visit. Variables will be pulled from [frmSURVEILLANCE_CONTACT] (field [ASSESS_VIS]= 'YES') and [frmSYMPTOMS_RTI] (fields [ASSESS_VIS]= 'Yes' and [sctSYMPTOMS_RTI]= 'BREATHING')

AND

(The data for below can be pulled from the Case Assessment Visit OR Worsening Visits. If worsening visits took place for this episode, the most severe value of SpO₂ or RR will be used, whether it was observed in the Case Assessment Visit or the Worsening Visit.)

- SpO₂(<95% if altitude ≤2500m and <92% if altitude >2500m) during the physical examination of case assessment visit. (field [scOXYGEN_SATURATION_RTI] OR [scOXYGEN_SATURATION_WOR]=[SpO₂]< '95.0%' or <92%)
OR
- RR increase (field [sctRESPIRATORYRATE_RTI]=[VSORRES_RESP] OR [sctRESPIRATORYRATE_WOR]=[VSORRES_RESP_WOR])

RR increase defined as:

- > 60/minute (< 2 months of age)
- > 50/minute (2 to < 12 months of age)
- > 40/minute (12 to 24 months of age)

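### The LRTI entry symptoms are read only from the case-assessment forms, against the SAP's own rule that symptoms from worsening visits are combined, so some LRTI cases can go uncounted

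*SAP*

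**What the plan says.** All references are to the current SAP text (Amendment 2).

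- **Section 9.4, general rule.** Where a worsening visit occurs, "all symptoms collected from the initial visit and the worsening visit(s) are combined and counted under one episode", and the most severe level is used for the derivation. The forms listed for a worsening visit are frmWORSENING_INFO and frmVITALSIGNS_WOR.
- **Section 9.4.2, entry symptoms.** The infant must have "at least one of the following symptoms: (The data can be pulled from the Case Assessment Visit". The cough and difficulty-breathing bullets cite only frmSURVEILLANCE_CONTACT and frmSYMPTOMS_RTI.
- **Section 9.4.2, objective criterion.** For SpO2 and respiratory rate the wording changes: "The data can be pulled from the Case Assessment Visit OR Worsening Visits". Worsening fields are listed beside the case-assessment fields.
- **Section 9.4.7, all-cause LRTI.** Same split. The second entry bullet begins "Difficulty breathing reported during the case assessment visit".
- **Sections 9.4.3 and 9.4.4.** "RSV severe LRTI cases will be reported if the person meets the case definition of RSV LRTI"; "RSV very severe LRTI is defined as meeting the case definition of RSV LRTI". Their SpO2 criterion, and chest indrawing for severe LRTI, may come from a worsening visit.
- **Sections 9.4.2.1, 9.4.2.2, 9.4.7.1 and 9.4.7.2.** Start and end dates use the case-assessment symptom fields only.
- **Section 2.1, sampling.** "for each RTI with suspicion of difficulty in breathing, or wheezing, or with parental concern, a nasal swab will be collected".

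**The concern.** A programmer who follows 9.4 and one who follows 9.4.2 can produce different case lists from the same data. The criterion in dispute gates all three severity tiers, so a worsening-visit SpO2 or indrawing value cannot rescue an infant who fails it.

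The incidence of all, severe and very severe RSV-LRTI is a secondary objective (section 3.2.1). The same cases feed the Cox models on cord-blood antibody (section 5.4.2.2), and all-cause LRTI is also reported (section 5.3.6.2). Section 2.1 ties the worsening form to a child who has deteriorated and is admitted or needs oxygen. The episodes in question are therefore ones a study meant to inform later RSV trials would want to classify correctly.

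**Working it through.** The SAP gives no figure on this point, so there is none to reproduce. The check is of the logic.

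**1. Can the situation arise?** A swab visit may follow parental concern alone (section 2.1), and an RTI may be a runny or blocked nose without cough (Table 3). An infant can therefore be assessed with neither entry symptom. If symptoms worsen within 7 days, the infant has a worsening visit (section 9.4.8). A new case assessment form opens only for new cough or blocked nose after 7 days from the last RTI symptom end date (section 9.4). The SAP provides no second case assessment within that episode.

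**2. The two rules, with RSV confirmed.** Let S be the entry criterion (cough or difficulty breathing) and O the objective criterion (SpO2 or respiratory rate), each observed at the case assessment (1) and at the worsening visit (2).

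- Section 9.4.2 as written: case if S1 and (O1 or O2).
- Section 9.4 as written: case if (S1 or S2) and (O1 or O2).

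Four yes/no items give 2 × 2 × 2 × 2 = 16 patterns. The rules differ only when S1 is absent, S2 is present, and at least one of O1 and O2 is present:

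| S1 | S2 | O1 | O2 | 9.4.2 | 9.4 |
|---|---|---|---|---|---|
| no | yes | no | yes | not a case | case |
| no | yes | yes | no | not a case | case |
| no | yes | yes | yes | not a case | case |

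That is 3 of 16, all in one direction. The patterns are not equally likely, so 3/16 is a count of disagreements and not an estimate of cases lost.

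**3. Effect on the severity tiers.** Illustration: an RSV-positive infant at a site at or below 2500 m is assessed for runny nose with parental concern. At a worsening visit in the same episode the infant has cough, difficulty breathing and SpO2 88%.

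- Under 9.4.2: S1 is absent, so no LRTI, and hence no severe or very severe LRTI.
- Under 9.4: LRTI (88 < 95), severe LRTI (88 < 93) and very severe LRTI (88 < 90).

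**4. Dates.** Opening the entry criterion alone would not be enough. The start and end date rules read the case-assessment symptom fields, so a case that qualifies through a worsening visit would have no LRTI onset or end date.

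**5. Can pooling be programmed?** Neither worsening form named in 9.4 is shown to hold a cough or difficulty-breathing item. However, 9.4.3 reads chest indrawing from a worsening field (sctCHEST_INDRAWING_WOR), and Table 3 footnote 1 lists chest in-drawing among the signs of difficulty in breathing. Pooling is therefore at least partly possible. That footnote is based on parental history while the worsening field records a finding, so the SAP would have to state that the field counts.

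**The case against.** The strongest reply is that no contradiction exists in practice. Section 9.4 pools what is collected, and the SAP does not show cough or difficulty breathing being collected at worsening visits; 9.4.2 would then simply use the fields available. The case assessment form may also be an episode-level record: 9.4.2.2 takes symptom end dates from it, which often cannot be known at a visit within three days of onset, so a later symptom might be added there. And the visit wording is loose, since the SpO2 bullet also mentions the case assessment visit while listing a worsening field.

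Part of this stands. The SAP does not settle what the worsening forms hold or whether late symptoms are added to the first form. But it does not say that they are added, and the field lists are not loose: SpO2 and respiratory rate each have a worsening field, the entry symptoms have none. If the data are absent, the statement in 9.4 that all symptoms are combined is wrong and needs correction.

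Three stronger readings are tempting and are not supported:

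- *An infant first seen with wheeze is lost.* Table 3 footnote 1 counts wheeze as difficulty in breathing, so that infant already meets the entry criterion as defined. The clear route is parental concern with nasal symptoms only.
- *Such an infant can never be a case.* The exclusion holds within that episode and on the literal reading of 9.4.2. A later episode can qualify, and an admitted RSV-positive infant still counts under RSV hospitalization (section 9.4.5), which has no symptom gate.
- *A given percentage of cases is lost, with severe disease hit harder.* The SAP supplies no attack rate, severe share or frequency of late entry symptoms, so any such percentage would rest wholly on assumed inputs.

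**Conclusion.** The point holds as a contradiction between the general rule in 9.4 and the specific derivations in 9.4.2 and 9.4.7, carried into the severe and very severe tiers by nesting. On the literal reading of 9.4.2 the direction is undercounting. One entry symptom at the first assessment is enough to qualify, and two of the three swab triggers are themselves breathing signs, so the affected group is probably small; its size cannot be derived from the SAP. The conclusion assumes that the case assessment fields are not updated with symptoms arising later. It is worth fixing because the rule decides who is a case and the change is cheap.

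**What to change.** Reconcile 9.4, 9.4.2 and 9.4.7 as follows.

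- Let the entry criterion be met at the case assessment visit or at any worsening visit of the same episode. Name the worsening-form fields that supply it, for example the chest-indrawing field, and state that it counts as difficulty in breathing under Table 3 footnote 1.
- Align 9.4.2.1, 9.4.2.2, 9.4.7.1 and 9.4.7.2 so that a symptom first recorded at a worsening visit can supply the start or end date.
- Report how many cases qualify only through a worsening visit, by severity tier.

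If the worsening forms hold no usable item, correct the pooling statement in 9.4 to say so, and report the number of infants who met the SpO2 or respiratory-rate criterion but lacked the entry symptom at case assessment. That number bounds the possible undercount.

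The cost is wording in the general rule, two derivations and their date rules, plus a small programming change. No new data collection is needed.
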